**Mechanical Temporal Summation.** Temporal summation of pain will be assessed using repetitive mechanical stimuli. The assessment of temporal summation involves rapidly applying a series of identical noxious stimuli and determining the increase in pain across trials; animal studies have suggested that temporal summation occurs centrally in second-order neurons in the spinal cord as a consequence of sustained C-fiber afferent input (149-151). For temporal summation of mechanical pain, pain ratings in response to a single punctate noxious stimulus will be compared to pain ratings in response to a sequence of identical punctate noxious stimuli (152). A weighted pinprick stimulator with a flat contact area will be used to deliver either a single pinprick stimulus or a train of 10 pinprick stimuli repeated at a constant rate. Following the single stimulus and the 10-stimulus train, the subject is asked to give a pain rating. Single pinprick stimuli are alternated with the trains of 10 stimuli. Similar procedures using this type of weighted pinprick stimulator have been used in diabetic neuropathy (153), healthy subjects (154), and to assess temporal summation (155-156).

**Acute Effects of Hydromorphone:** Participants will ingest medication under staff supervision and complete a battery of self-report, physiological, and cortisol measures will be collected prior to dosing and up to 15 time points post-dose (up to 6 hours). During the final assessment each day, participants will complete a Drug vs. Money Questionnaire modeled from the Multiple Choice Procedure to indicate the dollar value they would place upon the drug received and this measure will be repeated immediately prior to the next day's drug administration. These experimental procedures are consistent with those used in a previous study by our group (110). Participants will be discharged from the study on the final day after completing the final study assessment and a field sobriety test that indicates no persistent opioid effects. We will conduct a follow-up phone call with participants the day following discharge to document any adverse events and to administer the final Drug vs. Money Questionnaire.

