Hydromorphone hydrochloride is a pure mu opioid agonist that can be administered in oral, rectal, intramuscular (IM), or intravenous (IV) formulations for the indication of acute and/or chronic pain. We have chosen to administer hydromorphone orally in this study to reduce the potential for side effects and adverse events associated with the more direct parenteral administration, and to increase the clinical relevance of the study by administering the most commonly-abused formulation of hydromorphone. This will also extend the time course of hydromorphone effects, which will help us to achieve our study aims. When administered orally, hydromorphone is rapidly absorbed through the gastrointestinal tract and subjected to extensive first-pass metabolism. Exposure to hydromorphone is proportional to the dose range, with *in vivo* bioavailability of an 8mg tablet being approximately 24%. Following oral administration, peak plasma level of hydromorphone is generally attained in 30 – 60 minutes, and approximately 95% of hydromorphone is metabolized to hydromorphone-3-glucuronide via glucuronidation in the liver. There is no apparent effect of sex on the pharmacokinetics of hydromorphone.

- c. Justification and safety information if non-FDA approved drugs without an IND will be administered.

N/A

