**Association Model:** Our primary goal is to demonstrate the impact of SNP variation across OPRM1 on variability in response to hydromorphone across time and dose. Association analyses will be performed by modeling genotype at each SNP in a general linear model. In its simplest form this test, commonly termed the measured genotype analysis (137), models the influence of genotypic variation at a given locus on variation in the quantitative trait, essentially a one-way Analysis of Variance (ANOVA). This approach provides a distinct advantage in that it can easily be extended to a two-way ANOVA to model genotype effects across 3 different doses of drug. In addition, the flexibility of the GLM allows incorporation of ancestry covariates and environmental moderators or mediators. We will examine the impact of OPRM1 at each time-point in separate analyses and account for the multiple testing using LD-adjusted Bonferroni correction (see below).

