**Analysis of pain testing sessions:** We hypothesize that OPRM1 SNP variants will exhibit greater pressure pain thresholds, greater CPM efficiency, lower hydromorphone-related analgesia, and lower cortisol stress response than participants with the major allele, and that results will be positively correlated with response to self-report and physiologically-mediated hydromorphone drug effects collected during days 3-5. Pressure pain threshold will be estimated by averaging the results of the 2 administrations to radiobrachialis and quadriceps muscle groups. We will generate a CPM index for each participant [(mean pressure pain threshold during cold pressor)/(mean pressure pain threshold prior to cold pressor)] x 100 (90). These values will provide a quantitative measure of percent change in the test stimulus (i.e., pressure point threshold). Mixed effects regression models with a random intercept will be used to compare dependent variables (pressure pain threshold, DNIC threshold, DNIC index) as a function of within-subject drug effects (placebo vs. hydromorphone), and between-subject effects of OPRM1 SNP analysis will be conducted as specified in Aim 1. Gender, age, and race have been associated with response to pain and the CPM test (146-148). Gender will be evaluated using independent subgroup analyses and age and race will be included as covariates. Finally, subscale scores of self-report measures of pain and coping strategies will be compared between the two genotype groups using independent samples t-tests, and drug identification data will be compared using a chi-square for each drug condition. We expect that both experimental manipulations will induce pain in the minor and major allele groups, and that participants with the minor allele will demonstrate lower sensitivity to pain (e.g., greater pressure pain magnitudes), lower NRS ratings of pain, lower cortisol response to painful stimuli, and lower analgesic relief from hydromorphone compared to the major allele participants.

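### The primary goal covers response over time, but the drug-effect curves are analysed one time-point at a time, with no genotype-by-time test and no time summary

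*Combined protocol and SAP*

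**What the plan says.** All references are to the combined protocol and SAP.

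- **Goal.** Section 7, Association Model: "Our primary goal is to demonstrate the impact of SNP variation across OPRM1 on variability in response to hydromorphone across time and dose".
- **Data.** Section 4, Acute Effects of Hydromorphone: self-report, physiological and cortisol measures are taken "prior to dosing and up to 15 time points post-dose (up to 6 hours". Section 7a lists high, liking, pupil diameter and blood pressure among the primary outcomes.
- **Time.** The Association Model paragraph ends: "We will examine the impact of OPRM1 at each time-point in separate analyses and account for the multiple testing using LD-adjusted Bonferroni correction".
- **Dose.** The same paragraph says of the genotype model that "it can easily be extended to a two-way ANOVA to model genotype effects across 3 different doses of drug".
- **Pain outcomes.** Section 7, Analysis of pain testing sessions, gives a mixed model with a random intercept. It is limited to pain measures, and its within-subject factor is drug. Section 4 schedules one pain session a day.
- **Power.** Section 7, Power and Correction for Multiple Testing, claims more than 80% power at an alpha of .001 for d of about .45 (N=100) and .67 (N=50). It says alpha must be adjusted for multiple time-points, but no number of time-points enters the calculation.

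**The concern.** The goal names two dimensions, and the stated method covers only one. A set of cross-sectional genotype tests shows whether genotype matters at a given minute. It does not show whether the genotype groups differ in onset, peak or duration, which is what an effect across time means. A result at one time and none at another is not evidence that the two times differ.

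The plan also does not say which of up to 15 results per outcome and SNP answers the primary hypothesis. Each test carries the noise of a single reading, because correlated readings from one person are never pooled. At stake are the interpretability of the main abuse-liability outcomes and, under some conditions, their power.

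**Working it through.** **1. Is there a time test anywhere in the plan?** For high, liking, pupil and blood pressure, the Association Model gives separate general linear models by time-point. The optional two-way ANOVA adds dose, not time. The pain mixed model covers other outcomes, measured in one session a day, so it cannot describe a time course. The power paragraph contains no time-points and no correlation over time. Nothing fills the gap.

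**2. The plan's own power figure.** Inputs from section 7: N=100 or 50, alpha .001, d=.45 or .67. Assumed: equal genotype groups (the most favourable split) and two-sided tests. Power = Φ(d·√(N/4) − 3.291).

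- N=100: .45 × 5 = 2.25, and 2.25 − 3.291 = −1.04, giving 14.9%.
- N=50: .67 × 3.536 = 2.369, and 2.369 − 3.291 = −.92, giving 17.8%.

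The stated >80% is not reproduced. Counting three active doses as independent observations gives 72.8% and 79.2%. Reading the figures as Cohen's f with two groups gives 86.1% and 88.1%. No variant uses the repeated times, so the time readings add nothing to the power statement. Why the figure does not reproduce is a separate matter.

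**3. Minimum detectable d at 80% power, flat effect.** Formula: (z for alpha + .842)/√(N/4) × √((1 + (m−1)ρ)/m), where m is the number of readings averaged and ρ is their correlation. The documents do not give ρ.

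| Test | N=100 | N=50 |
|---|---|---|
| One given time-point, alpha .001 | (3.291 + .842)/5 = .83 | 1.17 |
| One given time-point, alpha .05/(50 × 15) = .000067 | (3.988 + .842)/5 = .97 | 1.37 |
| Mean of 15, alpha .001, ρ=.5 | .826 × √(8/15) = .60 | .85 |
| Mean of 15, alpha .001, ρ=.7 | .826 × √(10.8/15) = .70 | .99 |
| Mean of 15, alpha .001, ρ=.9 | .826 × √(13.6/15) = .79 | 1.11 |

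At ρ=.9 averaging itself gains little (.83 to .79). Most of the difference from .97 is then the cost of testing 15 times.

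**4. Power to find any hit, by simulation.** Settings: 50 versus 50, 15 readings, at least 3,000 replicates per setting. Separate t-tests are compared with one t-test at .001 on the mean of five readings. Correlation and curve shape are assumptions.

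| Setting | Separate tests | Five-reading mean |
|---|---|---|
| Flat d=.45, ρ=.5, alpha .001/15 | 24% | 33% |
| Flat d=.67, ρ=.5, alpha .001/15 | 74% | 83% |
| Flat d=.45, serial correlation .8, alpha .001/15 | 23% | 22% |
| Flat d=.67, serial correlation .8, alpha .001/15 | 75% | 71% |
| Peaked d=.67 (SD 2 readings), ρ=.5, window on peak, alpha .001/15 | 33% | 50% |
| Same, window three readings late | 33% | 6% |
| Flat d=.45, ρ=.5, alpha .001 not split | 58% | 33% |

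The last row is not a fair gain for separate tests. With no genotype effect, the chance of a hit per SNP can reach 15 × .001 = 1.5% (about 1.2% simulated), against .1% for the single test.

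**5. Apparent time-specificity.** With a truly flat effect, ρ=.5 and alpha .001/15, 73% of trials at d=.67 and 86% at d=.9 show some but not all time-points significant. At d=.45, about 76% show none.

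**The case against.** The strongest reply has four parts.

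- **Dose is not neglected.** A reader might infer that neither half of the goal is tested. The documents do not support that: the Association Model allows a genotype-by-dose ANOVA, and the power statement refers to the effect at each active dose. The wording is permissive and names no subject effect, but dose is provided for. This part stands.
- **Testing every time-point does examine genotype along the curve.** True, but only point by point. The missing piece is a contrast between times or a summary over them. A reader might also infer that the investigators intend to read a time pattern from which points reach significance. The plan never says so.
- **Lower power is not established.** This stands as a limit. It follows only if alpha is divided over the time-points. The plan states that intention but gives no count, and its only numerical alpha is .001. Even with the division, the gain depends on an unstated correlation and curve shape.
- **A fixed peak window is hard to place.** This also stands. Section 6b says that "peak plasma level of hydromorphone is generally attained in 30 – 60 minutes", which concerns plasma level and not effect. Section 4 (Delay Discounting) places peak drug effects at 30 minutes. The reading times are not listed. A window tied to the 60-90 minute pain session would mix pain stimulation into blood pressure and pupil readings.

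**Conclusion.** The concern holds for time only. As written, no analysis of the primary drug-effect outcomes can test a genotype difference in time course, and none combines a person's readings within a session. This follows from the text and does not depend on any assumed correlation.

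A flat statement that the plan loses power would go too far. If alpha is split over 15 time-points, the simulated change runs from a gain of 9 points (24% to 33%, flat d=.45, ρ=.5) or 17 points (33% to 50%, peaked d=.67, window on the peak) to none under serial correlation. It becomes a loss of 27 points (33% to 6%) when the window is three readings late. All of these rest on equal genotype groups and assumed correlations and curves.

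This is a correctable mismatch between goal and method that should be fixed before analysis.

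**What to change.** Replace the last sentence of the Association Model paragraph along these lines:

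- For each primary drug-effect outcome, fit a repeated-measures mixed model containing genotype, time, genotype-by-time and dose. Keep the ancestry covariates already planned. State a within-person covariance for readings within a session and across sessions.
- Test per SNP at the SNP-adjusted alpha, and name in advance which term carries the primary test.
- Base any time-course claim on the genotype-by-time term. Report individual time-points descriptively.
- If a single-value primary test is preferred, pre-specify one summary per person, such as peak effect or a post-dose window mean, before genotype data are seen. Justify it from the time course of drug effect, not from the timing of the pain session.

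The cost is SAP wording and a modest amount of modelling, with no new data or visits. The downsides are a covariance assumption and less weight on an effect confined to one time-point. If a window is chosen, it may also be misplaced.

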
#### 2. Objectives (include all primary and secondary objectives).

The primary aim of this study is to examine the associations of specific polymorphisms in the OPRM1 gene with mu opioid receptor (MOR)-mediated effects. We hypothesize the minor A118G SNP allele and OPRM1 tagging SNPs will predict more reinforcing properties of hydromorphone, (e.g., higher self-report ratings of high and drug-liking) and greater opioid-induced physiological changes (e.g., pupil diameter, blood pressure), decreases in cortisol levels as a function of the degree of pleasant effects of hydromorphone, and steeper discounting curves on a delay-discounting task. The secondary aim of this study is to examine the associations of specific polymorphisms in the OPRM1 gene with laboratory measures of pain. We hypothesize the minor A118G SNP allele and OPRM1 tagging

SNPs will predict higher pain threshold on two experimentally-induced laboratory measures of pain, lower analgesic efficacy in response to experimentally-induced pain, and lower cortisol response to painful stimuli. Finally, as an exploratory aim, we will examine the contribution of sex to the primary and secondary aims.

**3. Background** (briefly describe pre-clinical and clinical data, current experience with procedures, drug or device, and any other relevant information to justify the research)

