## 7. Study Statistics

a. Primary outcome variables. The primary outcome variables are self-reported ratings of drug high and liking, changes in pupil diameter and blood pressure, pain threshold on 2 laboratory measures of pain, and analgesic efficacy in response to laboratory-induced pain. We expect that individuals with the minor allele of the A118G SNP and other

tagging SNPs across the OPRM1 gene will find hydromorphone more reinforcing (e.g., higher self-report ratings of high and drug-liking) and exhibit greater opioid-induced physiological changes (e.g., pupil diameter, blood pressure). Research also suggests the OPRM1 gene may also confer greater sensitivity to the negative effects of opioids, which may be observed as measuring greater ratings of nausea. We also hypothesize the minor allele and other tagging SNPs across the OPRM1 gene will produce higher pain threshold on 2 laboratory measures of pain, and lower analgesic efficacy in response to laboratory induced pain.

**b. Secondary outcome variables.** Decreases in cortisol levels as a function of the degree of pleasant effects of hydromorphone and painful stimuli, delay-discounting curves, and the effect of sex on all outcome measures. We hypothesize that individuals with the minor alleles will have greater decreases in cortisol levels as a function of the degree of pleasant effects of hydromorphone, lower cortisol in response to painful stimuli, and steeper discounting curves on a delay-discounting task. Finally, although we expect that the A118G will be associated with these effects, we hypothesize that several of the additional OPRM1 tagging SNPs will contribute to effect magnitude.

**c. Statistical plan including sample size justification and interim data analysis:** The aims of the proposed study will explore the impact of genetic variation across the OPRM1 gene on hydromorphone response. There are specific steps we describe below to assure that we interrogate all known functional variation across the OPRM1 gene, adequately cover all other variation using appropriately selected tagging SNPs, prevent spurious associations due to population stratification by accounting for local ancestry, and properly control the Type I error rate.

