**Power and Correction for Multiple Testing:** Power (1-Type II error) and correction for multiple testing (control of Type I error) are important considerations in any genetic association study. Typically investigators attempt to control the Type I error rate of a given set of hypothesis tests by controlling the family wise error rate through manipulation of the alpha level of the test. This is not problematic when a handful of tests are performed at an alpha level (false positive level) of 5%, where the usual approach is the Bonferroni correction. We anticipate performing tests across multiple time-points and must adjust our target alpha level. Importantly, our 71 selected SNPs across the OPRM1 gene (see below) do not represent 71 independent tests due to correlation between SNPs. We will use an approach, termed SNPSpD (138) which uses spectral decomposition to estimate the number of independent tests across the region. Using available HapMap data, we estimate 44 independent tests across the region. We calculate power for the GLM approach modeling the effect of genotype on phenotype. If we assume a constant effect size difference between genotype groups (at each dose other than placebo), at an alpha level conservatively adjusted for 50 tests to .001, using the entire completer sample (N= 100) or the sex subsamples (N=50), we have >80% power for modest effect sizes of ~.45 and .67 respectively. In our calculations, effect size (Cohen's d) is the mean difference between genotype groups in standard deviation units. Importantly, this effect size is well within the range seen by other studies examining drug response difference in OPRM1 (e.g., Ray et al., 2004: effect size = 1.2).

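### One .001 threshold serves the pooled sample and each sex, sex carries two labels, and no rule says whether a finding in one sex alone counts

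*Combined protocol and SAP*

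**What the plan says.** All references are to the combined protocol and SAP.

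- **Threshold (7c, Power and Correction for Multiple Testing).** The power statement sets one level, "adjusted for 50 tests to .001, using the entire completer sample (N= 100) or the sex subsamples (N=50" each. No other level is given for the sex analyses.
- **What the 50 covers (same paragraph).** The 71 SNPs are reduced by spectral decomposition: "Using available HapMap data, we estimate 44 independent tests across the region". That leaves room for six more tests and contains no factor for three analysis sets.
- **Status of sex.** Section 2 says "as an exploratory aim, we will examine the contribution of sex to the primary and secondary aims". Section 7b includes among the secondary outcomes "delay-discounting curves, and the effect of sex on all outcome measures".
- **Pain outcomes (7c, Analysis of pain testing sessions).** "Gender will be evaluated using independent subgroup analyses and age and race will be included as covariates". Section 3 describes the sex effect on pain as robust.
- **Decision rule.** No section says which analysis settles a genotype hypothesis, or how the error allowance is shared among the pooled, male and female analyses.

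**The concern.** Each SNP may be tested up to three times on the same outcome: in all completers, in men and in women. The allowance of 50 tests is roughly one pass through the gene. Without a rule on which pass counts, an association seen in one sex only could be reported as an OPRM1 finding at a level meant for a single pass. The choice among the three could be made after the results are known. The introduction to 7c undertakes to control the Type I error rate, and the two labels for sex leave open whether that undertaking covers the sex-specific tests.

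A smaller point concerns the pain models. Age and race are named as covariates and sex is not. If a pooled pain model is fitted without sex, the variation between men and women stays in the error term.

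**Working it through.** **Inputs from the plan.** Family level 5%; 50 tests allowed for; 44 effective SNP tests; pooled N=100 and sex subsamples of 50.

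**Assumptions not in the plan.** Two-sided tests, no true effect, tests independent after reduction to K = 44 (or K = 50), equal numbers of men and women. Everything below is for one outcome at one time-point.

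**1. The plan's level.** .05/50 = .001, which reproduces.

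**2. One analysis set.** Rate = 1 - (1 - .001)^K.
- K = 44: 1 - .999^44 = 4.3%
- K = 50: 1 - .999^50 = 4.9%

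**3. The two sex-specific sets only.** Men and women are independent samples, so there are 2K tests.
- K = 44: 1 - .999^88 = 8.4%
- K = 50: 1 - .999^100 = 9.5%

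**4. Pooled plus both sexes.** The pooled statistic overlaps with each sex: z_pooled = (z_men + z_women)/√2, a correlation of .71 with each. Numerical integration gives a probability of .00271 per SNP that at least one of the three exceeds the .001 cut-off.
- K = 44: 1 - (1 - .00271)^44 = 11.3%
- K = 50: 1 - (1 - .00271)^50 = 12.7%

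This is about 2.6 times the single-set rate (11.3/4.3; 12.7/4.9). A 30:70 sex split gives 11.0% to 12.4%. Ignoring the overlap, the simple bound is 132 × .001 = 13.2% to 150 × .001 = 15.0%.

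**5. A level covering all three sets.** .05/(3 × 50) = .00033 per test gives 4.0% (K = 44) to 4.5% (K = 50). Using the overlap, .00042 (K = 44) or .00037 (K = 50) gives exactly 5%.

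**6. Power at the stricter level.** With equal genotype groups and the three active doses treated as independent observations (a favourable assumption), two-sided power falls as follows between .001 and .00033:
- d = .45, N=100: 73% to 62%
- d = .67, N=50: 79% to 70%

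The starting values are below the plan's stated figure of over 80%. They are used here only to show the size of the loss.

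**7. Sex as a covariate.** Suppose the sexes differ by d within-sex SDs. The share of variance explained is R² = (d²/4)/(1 + d²/4), and the genotype standard error is multiplied by √(1 - R²).
- d = 0.6: R² = .09/1.09 = .083, ratio .958
- d = 0.8: R² = .16/1.16 = .138, ratio .928
- d = 1.0: R² = .25/1.25 = .200, ratio .894

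The cut is therefore about 4% to 11%. The range for d is assumed; the plan gives no figure. It applies to comparisons of pain threshold between persons. In the within-person contrast of hydromorphone with placebo, a constant sex difference cancels, so there is little or no gain.

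**The case against.** The strongest reply is that the subsample threshold appears in a power statement and not in a decision rule, and that section 2 calls sex exploratory. On that reading the pooled test alone supports claims and the rate is 4.3% to 4.9%. This stands as far as it goes: nowhere does the plan say that a finding in one sex would count equally with a pooled one. But 7b says secondary, the paragraph in question also deals with correction for multiple testing, and it offers no other level for the sex analyses. The plan does not settle the matter. The mention of gender in the Benefits section adds little, since an objective can be exploratory.

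A second reply is that three tests per SNP are not established for pain. If gender is handled only by subgroup, there are two tests and the figure is 8% to 10%. If a pooled pain model is fitted, the Aim 1 model to which that paragraph refers allows covariates and moderators. Omission of sex is thus an inference from the two covariates named, not something stated. Both points stand, and the covariate advice is a small improvement, not the correction of a demonstrated error.

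A reader might also infer that the study's chance of a false OPRM1 claim is 11% to 13% where 5% was promised. The documents support neither figure as a study-wide rate. Section 7c tests each time-point separately, section 4a allows up to 15 post-dose time-points, and 7a names several primary outcomes. Treating 15 time-points as independent, the pooled analysis of one outcome could by itself reach 1 - .999^660 = 48% (K = 44) to 1 - .999^750 = 53% (K = 50). The true value is lower because time-points are correlated, by an amount the plan does not give. Settling the role of sex does not address that.

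**Conclusion.** The point holds in conditional form. The plan gives the pooled sample and each sex the same .001, labels sex in two incompatible ways, and does not say whether sex-specific hits are findings. If they are, and a pooled test is also run, the false-positive rate per outcome and time-point is up to about 11-13%, against 4-5% for the pooled test alone. If they are not, no inflation comes from this source. The figures rest on two-sided tests and on 44 to 50 independent tests; they change little with the sex split. The precision gain from a sex covariate rests on an assumed sex difference and is confined to between-person threshold comparisons. Clarification before analysis is worthwhile because it removes a choice among three analyses at little cost.

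**What to change.** - In 7c, state that the pooled N=100 analysis decides each genotype hypothesis.
- Carry the exploratory label from section 2 into 7b. Report sex-specific results as estimates with confidence intervals and no significance claim.
- Name sex as a covariate beside age and race in the pooled pain models.

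The cost is a few sentences and one covariate that is already collected. The real downside is that a result in one sex can no longer be claimed as significant on its own.

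If the sponsor wishes to keep such claims, all three analysis sets belong in the correction, at about .00033 to .0004 per test, and the power statement should be redone at that level. Power will be lower, by roughly 9 to 11 percentage points under the favourable assumption used above.

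Either way, multiplicity over time-points and outcomes needs its own rule.
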